4 STUDY DESIGN

4.1 Identification of Study Design

MTN-003-P01 is a three-arm, randomized, placebo-controlled, double-blinded pilot study of Wisebag for monitoring daily product use. The study is double-blinded with respect to participants and investigators, (but not for pharmacy and information technology (IT) staff who will manage the download of the electronic data and the battery charging of Wisebag devices). Approximately 50 participants will be randomized to the 3 study arms in a 1:2:2 ratio. The 3 groups will be “dummy” Wisebag (n~10) “Online device” Wisebag (n~20), or “Offline device” Wisebag (n~20).

There will be two study visits: an enrollment visit and one follow-up/exit visit, two weeks after enrollment. During study participation, participants will be asked to open their assigned Wisebag at approximately the same specified time daily, to peel off one sticker from a set of study stickers inside the bag, and place the sticker on the appropriate day of the week on a study provided diary card. After two weeks of daily openings, participants will be asked to return to the study clinic for an exit visit with their Wisebag and diary card.

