7.1 Screening and Enrollment

The Screening and Enrollment Visit for the Wisebag pilot should take place within approximately 4 weeks of the last VOICE Screening Visit; however participants may be enrolled up to 90 days after the date of the last VOICE Screening Visit. Screening for all data collection activities will include oral or written confirmation that participants meet the inclusion and exclusion criteria. Study staff will create checklists to ensure this is consistently documented.

Table 1: Screening and Enrollment

Screening and Enrollment	
Component	Procedures
Administrative and Regulatory	
 • Obtain informed consent • Confirm eligibility • Obtain locator information • Randomization • Schedule next (exit) visit • Provide counseling regarding protocol adherence • Provide reimbursement for study visit
Behavioral	
 • Conduct demographic and brief behavioral assessment • Dispense (2) weekly diary cards as well as the Wisebag along with instructions on use. • Practice opening/closing the bag and placing a study sticker on their diary card

7.2 Exit Visit: End of Week 2

Visit window at target exit visit date: The target visit exit date will be 2 weeks (14 days) from the enrolment date, with an allowable visit window of plus or minus 3 days. Participants who present late for their exit visit (Day 18 or later) will complete study procedures, as long as the study is still in the accrual phase. Otherwise, the participant will be classified as lost to follow up if they missed the exit visit window and there were 3 unsuccessful contact attempts.

Table 2: Exit Visit: End of Week 2

Week 3	
Component	Procedures
Administrative and Regulatory	
 • Collect Wisebag from participant. • Download data from the 2 week period from all “active” Wisebags • Provide reimbursement for study visit • Debrief on the full purpose of the research
Behavioral	
 • Conduct behavioral and acceptability assessment • Collect and review diary card • Semi-structured brief qualitative interview • Perceived Wisebag product

7.3 Interim Visits:

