Interim visits may be performed at any time from enrollment to Day 10 for the reasons listed below. Interim visits after Day 10 (and before Day 14) will be in the Exit visit window and an Exit visit will be conducted in lieu of an interim visit. All interim contacts and visits will be documented in participants' study records and on applicable CRFs.

- For administrative reasons, e.g., a participant may have questions for study staff, or may need to re-schedule a follow-up visit.

- For Wisebag use or data collection related reasons, e.g., a participant may need additional stickers, a new diary card or a replacement Wisebag because of malfunction (e.g. the zipper is broken), loss or theft.
- In response to social harm or safety concerns. Although this is not expected to happen, given the minimal risk associated with this study, participants will be told to come to the study in case such an unexpected event happens. In such occasion, study staff will assess the reported event clinically and provide or refer the participant to appropriate medical or psychological care as required.
- For other reasons at participant request.

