10.3 Primary Study Hypotheses

This is primarily an exploratory descriptive study that is not designed to test a hypothesis. However, the objectives of the study are based on the assumption that the "active" Wisebags will successfully and accurately record opening events, and will be acceptable for use by

women in the study, and that women will not be able to distinguish between an active and dummy Wisebag.

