10.5.2 Data Analysis

Performance endpoint

Performance will be assessed by comparing the number of failures (e.g., difficulties downloading stored data or receiving wireless data, battery- or signal-failures) experienced in each of the active-device groups. Questionnaire data reporting participants' user-related problems with the bag, device and/or battery will be tabulated overall and by randomization assignment. As indicated by the distribution of data, count data may be recoded and analyzed as categorical data. Count data will be compared using Poisson regression while categorical data will be compared using Chi-square tests. In cases of skewed data, alternative regression models may be implemented as appropriate.

Ability to Identify Randomization Arm

To assess blinding, the proportion of participants who are able to accurately identify whether they were randomized to the "dummy" or active-device groups will be reported. The proportion of participants who are able to indicate whether a demonstration bag is "dummy" or active (note that offline and online devices are identical, aside from the SIM card inside the online device), upon visual inspection, will also be reported. A summary statistic, such as the Cohen's kappa coefficient, will be used to summarize a) the level of agreement between the participant's response and the true group assignment and b) the level of agreement between the participant's response and the true bag type.

Concordance endpoint

Concordance between signal data and diary data will be summarized for participants assigned to the active device groups, and analysis will include the following: the proportion of participants whose number of events per signal data equals, exceeds, or is lower than the number of events per diary data. No formal testing will be performed on this endpoint.

Feasibility and acceptability endpoint

Feasibility and acceptability data collected at study exit by questionnaires will be summarized overall and by randomization group. No formal testing will be performed on this endpoint. Open-ended interview data will be tabulated, thematically coded and summarized by randomization group.

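### Plain Poisson regression is the default for online-offline failure counts, so repeat failures of one faulty bag can be taken as independent evidence

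*Protocol*

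**What the plan says.** Comparing the technical performance of the offline and online functions is the first primary objective (Protocol Section 3.1). Section 10.5.2 sets the measure: "Performance will be assessed by comparing the number of failures" in each active-device group, with download, reception, battery and signal problems as examples. It then names the methods: "Count data will be compared using Poisson regression while categorical data will be compared using Chi-square tests".

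Two clauses allow departures from that default. The sentence before it reads "As indicated by the distribution of data, count data may be recoded and analyzed as categorical data". The sentence after it reads "In cases of skewed data, alternative regression models may be implemented as appropriate".

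Section 2.4 describes a control signal sent once a day to show that the battery works. Section 4.2 includes that heart-beat signal in the technical performance endpoint. Neither section, nor 10.5.2, says whether a fault lasting several days on one bag is one failure or several.

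Section 10.5.2 rules out formal testing for the concordance and acceptability endpoints. It does not do so for performance.

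**The concern.** A dead battery or a lost signal tends to persist. If each missed heart beat is a failure, a bag that breaks early adds many failures to its arm's total, and all of them come from one event on one device. Plain Poisson regression treats them as separate pieces of information. Its standard error depends only on the arm totals, so it ignores how unevenly the failures are spread over bags.

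At stake is the comparison that informs which version of the bag to take forward. With about 20 women per active arm, a few persistently faulty bags falling by chance in one arm could be reported as a clear difference between modalities, with an interval that is too narrow.

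**Working it through.** The protocol states no error rate, failure rate or dispersion for this comparison, so there is no figure of its own to reproduce.

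**Inputs from the protocol.** "Approximately 50 participants will be randomized to the 3 study arms in a 1:2:2 ratio" (Section 4.1), which gives about 20 online and 20 offline. Follow-up is about 14 days, so a daily signal can be missed up to about 14 times.

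**Assumptions.** Two-sided 5% level. A bag is faulty with probability p = 10%, 20% or 30%, the same in both arms. A faulty bag logs a number of failures drawn uniformly from 1 to K, with K = 1, 3 or 14. Other bags log none.

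**Overdispersion.** The mean count is p(K+1)/2 and the mean square is p(K+1)(2K+1)/6. Hence

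variance/mean = (2K+1)/3 − p(K+1)/2.

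At p = 20%:
- K = 1: 3/3 − 0.2 = 0.80
- K = 3: 7/3 − 0.4 = 1.93
- K = 14: 29/3 − 1.5 = 8.17

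The Poisson standard error is too small by a factor √(variance/mean): √1.93 = 1.39 and √8.17 = 2.86.

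**Large-sample rejection rate under no difference**, 2[1 − Φ(1.96/√(variance/mean))]:
- K = 1: 1.96/0.894 = 2.19, giving 3%
- K = 3: 1.96/1.39 = 1.41, giving 16%
- K = 14: 1.96/2.86 = 0.69, giving 49%

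**Simulation at the actual size** (20 vs 20, no true difference, 100,000 trials per cell; for Wald, an arm with no failures counts as no rejection). Rejection rates for p = 10% / 20% / 30%:

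| Failures per faulty bag | Poisson, likelihood ratio | Poisson, Wald | Any failure yes/no, Chi-square |
|---|---|---|---|
| 1 | 8 / 5 / 3% | 0 / 0.5 / 1% | 4 / 5 / 5% |
| 1 to 3 | 26 / 18 / 15% | 4 / 12 / 13% | 4 / 5 / 5% |
| 1 to 14 | 56 / 51 / 48% | 34 / 48 / 48% | 4 / 5 / 5% |

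Other runs of the same scenarios differ by about one percentage point, so the last likelihood-ratio row is best read as 48% to 57%.

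**Alternatives for counts.** Permuting whole participants rejected in 1% to 5% of null trials for K = 3 and 14 (2,000 trials per cell). Quasi-Poisson with an F test rejected in 17 / 8 / 6% for K = 14, so it is not safe when faulty bags are rare.

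**The case against.** The strongest reply is that the protocol already allows the remedy. Zero-heavy, long-tailed counts are what would lead an analyst to recode to any failure yes/no, and the Chi-square test then holds its level at about 4% to 5%. Such counts are also skewed in the ordinary sense, so another regression model would be open. This stands as far as it goes. But both clauses are permissive, both are invoked after the data are seen, and neither is triggered by variance exceeding the mean. Low-mean Poisson counts are skewed even when the model is right, so skewness does not separate the good case from the bad one.

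A second reply is that daily recounting is assumed. That is correct. A download problem arises roughly once per bag, at the exit visit, and Section 7.3 allows a malfunctioning bag to be replaced, which would cut short a fault that is noticed. If each faulty bag counts once, there is no material problem.

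A third reply is that offsets, dispersion terms and counting rules commonly belong in the SAP, which is not at hand. Leaving them out is therefore not a fault. The point here is the model that the protocol does name as its default.

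A reader might infer three stronger things that the document does not support:
- **That the test simply has an error rate far above 5%.** The protocol fixes no significance level and gives no failure rate. For independent Poisson counts with means of 0.5 to 4, the rate is 4.1% to 5.4%.
- **That unequal follow-up is a joint cause.** The window of 14 ± 3 days (Section 7.2) is the same in all randomised arms and, without an offset, gives 4.1% to 6.1%. Higher rates, of 8.1% and 11.7%, need assumed late exits (10% of women at 18 to 42 days) together with mean counts of 2 and 4.
- **That naming a test contradicts Section 10.3**, which says "This is primarily an exploratory descriptive study that is not designed to test a hypothesis". An exploratory comparison is compatible with a study described as primarily descriptive.

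**Conclusion.** The concern holds conditionally. The stated default fits the endpoint badly if one device can contribute several failures, and the heart-beat signal makes that plausible. Under the assumptions above, the null rejection rate at a nominal 5% is about 15% to 26% (likelihood ratio) or 4% to 13% (Wald) with 1 to 3 failures per faulty bag. With 1 to 14 it is about 48% to 57% or 34% to 48%. The protocol does not say which form of the test would be used. The interval has the same fault whether or not a p-value is reported: at 20% faulty bags its standard error is too small by a factor of about 1.4 to 2.9.

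The exploratory status and the optional fallbacks lower the stakes. They do not make the default sound, and correcting it costs almost nothing.

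**What to change.** In Section 10.5.2, make the randomised participant, with her device, the unit of the main performance comparison. Report the proportion of participants with any failure in each active arm, and the difference with a 95% CI.

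If failure counts are also compared, replace plain Poisson regression with a permutation test that re-randomises whole participants. Robust or quasi-Poisson variance is an alternative when failures are not rare. If an alternative-model clause is kept, tie it to overdispersion rather than skewness.

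The change affects wording only, with no new data and no change of design. Intervals on counts become wider, and the main comparison loses some information on how often a faulty bag fails, which descriptive counts by arm can still show. The main interval will also be wide: at 20% in each arm, its half-width is about 1.96 × √(2 × 0.2 × 0.8 / 20) = 0.25, or 25 percentage points. A non-significant result should therefore not be read as equal performance.

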MTN Community Working Group (CWG) Representative

[name], R. H. Ed.

CWG Representative

FHI

[name]

[name]

[contact], [name]

[contact]

Email: [contact]

MTN-003-P01

The Wisebag Observational Pilot Study: Feasibility, Acceptability and Performance of an Electronic Event-based Monitoring System (Wisebag)

INVESTIGATOR SIGNATURE FORM

**Version 1.0
April 15, 2011**

A Study of the Microbicide Trials Network

**Sponsored by:
Division of AIDS, US National Institute of Allergy and Infectious Diseases
US National Institute of Mental Health
US National Institutes of Health**

I, the Investigator of Record (IoR), agree to conduct this study in full accordance with the provisions of this protocol. I agree to maintain all study documentation for a minimum of three years after submission of the site's final Financial Status Report to the US Division of Acquired Immunodeficiency Syndrome (DAIDS), unless otherwise specified by DAIDS or the Microbicide Trials Network (MTN) Coordinating and Operations Center. Publication of the results of this study will be governed by MTN policies. Any presentation, abstract, or manuscript will be submitted to the MTN Manuscript Review Committee, and made available to NIMH and DAIDS, for review prior to submission.

I have read and understand the information in this protocol and will ensure that all associates, colleagues, and employees assisting in the conduct of the study are informed about the obligations incurred by their contribution to the study.

Name of Investigator of Record

Signature of Investigator of Record _____
Date

MTN-003-P01

The Wisebag Observational Pilot Study: Feasibility, Acceptability and Performance of an Electronic Event-based Monitoring System (Wisebag)

PROTOCOL SUMMARY

- Short Title:** Wisebag Pilot Study
- Protocol Chair:** [name], PhD, MPH
- Sample Size:** Approximately 50 women
- Study Population:** Women who meet the MTN-003-P01 eligibility criteria, who screened out of a MTN-003 (VOICE) screening
- Study Site:** Site(s) in sub-Saharan Africa as designated by the MTN Executive Committee
- Study Design:** Three-arm, randomized, placebo-controlled, double-blinded pilot study of Wisebag for daily use. Women will be randomly assigned (1:2:2 ratio) to:
- Placebo Wisebag
 - Online device Wisebag
 - Offline device Wisebag

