10.4 Number of Participants

The approximate sample size per site is estimated in Table 3.

Table 3: Approximate Number of Participants per Group

Device Group	Number of Participants
Dummy	10
Online	20
Offline	20
TOTAL	50

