13.5 Informed Consent Process

Written informed consent will be obtained from each study participant prior to enrollment. In obtaining and documenting informed consent, the IoR and their designees will comply with applicable local and US regulatory requirements and will adhere to GCP and to the ethical principles that have their origin in the Declaration of Helsinki.

The Sample Informed Consent does not fully disclose the purpose of the study to participants, in particular participants are not told of the second primary objective to assess the success of the attempted blinding of the “dummy” vs. active Wisebag. **Disclosure of this objective may alter participants behavior toward the Wisebag (i.e., repeated openings of the bag or unintentional damage to the bag may occur because participants are curious about whether they can detect an active Wisebag).** The research could not practicably be carried out if this objective was disclosed to participants as behavior may be modified.

At the end of the study, participants will be notified of the full purpose of the study, including the ability of participants to detect a “dummy” vs. active Wisebag.

Study staff must document the informed consent process in accordance with the Requirements for Source Documentation in DAIDS Funded and/or Sponsored Clinical Trials (<http://rsc.tech-res.com/policiesandregulations/>). Participants will be provided with copies of the informed consent forms if they are willing to receive them.

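### Under 4:1 active-to-dummy allocation, the pooled percent correct on own assignment does not measure blinding success, and kappa does not show which arm was unmasked; guesses should be reported by arm

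*Protocol*

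**What the plan says.** Assessing whether the dummy bag was successfully blinded is the second of four primary objectives (Protocol 3.1). On allocation, section 4.1 states: "Approximately 50 participants will be randomized to the 3 study arms in a 1:2:2 ratio". Table 3 in 10.4 ("Approximate Number of Participants per Group") lists 10 dummy, 20 online and 20 offline.

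Section 7.5 describes two separate tasks at the exit visit. In the first, each woman says whether she thinks her own bag was a dummy or an active one. In the second, she is shown one dummy and one active demonstration bag and says which is which.

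Section 10.5.2 gives each task a proportion. For own assignment it is "the proportion of participants who are able to accurately identify whether they were randomized to the" dummy or active-device groups. For the second task it begins: "The proportion of participants who are able to indicate whether a demonstration bag is" dummy or active. Then: "A summary statistic, such as the Cohen's kappa coefficient, will be used to summarize" agreement for both tasks, the first being "the level of agreement between the participant's response and the true group assignment". The blinding paragraph mentions no breakdown by arm. In the same section, questionnaire-reported problems and acceptability are both to be summarised by randomization group.

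Section 13.5 adds that, at consent, "participants are not told of the second primary objective to assess the success of the attempted blinding of the" dummy versus the active bag.

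**The concern.** The own-assignment proportion pools two groups of very unequal size. A woman who has noticed nothing and says 'active' by default is right four times in five, because four bags in five are active. A high percentage may therefore reflect allocation and habit, not detection. Conversely, if every dummy user recognises her bag while active users are unsure, the percentage can look modest.

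Kappa is the natural correction. The question is whether it also restores what a reader of this objective needs to know: how far beliefs differed between dummy and active users, and in which arm. Section 2.4 explains the practical use: similar-looking bags for all vaginal-group women at a VOICE site, with data collected on only a subset. What dummy users came to believe bears directly on that use, and the planned summaries do not commit to showing it.

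**Working it through.** **Inputs.** Total about 50 at 1:2:2 (4.1); two-way own-assignment question, with no 'don't know' answer mentioned (7.5). The probability q of guessing 'active' is not in the protocol; it is an assumption, varied from 0 to 1.

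**Arm sizes.** 50 × 1/5 = 10 dummy; 50 × 2/5 = 20 online and 20 offline. Table 3 is reproduced. Active total 40, so the shares are 0.8 active and 0.2 dummy.

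**1. Pooled percent correct with no detection.** If both arms guess 'active' with the same probability q:

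percent correct = 0.8q + 0.2(1 − q)

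| q | Percent correct |
|---|---|
| 1.0 | 80% |
| 0.9 | 74% |
| 0.8 | 68% |
| 0.5 | 50% |
| 0.2 | 32% |
| 0 | 20% |

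With equal arms it would be 0.5q + 0.5(1 − q) = 50% at every q. The spread comes from the 4:1 split.

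**2. Kappa with no detection.** Kappa = (Po − Pe)/(1 − Pe), where Po is the proportion correct and Pe the agreement expected from the margins. When guesses are unrelated to arm, expected kappa is 0 for any q and any arm split. In 100,000 simulated trials at 10:40 the mean was about 0. The central 95% range was about −0.25 to 0.29 when 20% guess 'dummy', and −0.22 to 0.22 when 50% do.

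**3. Selected outcomes.** If d is the overall proportion saying 'dummy', Pe = 0.2d + 0.8(1 − d). The gap is the percentage saying 'active' among active users minus that among dummy users.

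| Row | Dummy users saying 'dummy' | Active users saying 'dummy' | Po | Pe | Kappa | Gap (points) |
|---|---|---|---|---|---|---|
| A | 0/10 | 0/40 | 0.80 | 0.80 | 0 | 0 |
| B | 10/10 | 10/40 | 0.80 | 0.56 | 0.55 | 75 |
| C | 5/10 | 0/40 | 0.90 | 0.74 | 0.62 | 50 |
| D | 10/10 | 20/40 | 0.60 | 0.44 | 0.29 | 50 |
| E | 2/10 | 2/40 | 0.80 | 0.752 | 0.19 | 15 |
| F | 10/10 | 25/40 | 0.50 | 0.38 | 0.19 | 37.5 |

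Worked example, row D: Po = (10 + 20)/50 = 0.60; d = 30/50 = 0.6; Pe = 0.12 + 0.32 = 0.44; kappa = 0.16/0.56 = 0.29.

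- A and B: same percent correct, with no dummy user and every dummy user naming her bag.
- C and D: same gap, but kappa 0.62 against 0.29. With 25:25 arms a 50-point gap gives kappa 0.50 whatever the guessing habit.
- E and F: same kappa (0.048/0.248 and 0.12/0.62, both 0.194), but gaps of 15 and 37.5 points. Percent correct is higher in E, where the gap is smaller.

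**4. By-arm summary.** With no detection the expected gap is q − q = 0 for every q and any arm split, and the two proportions show where detection occurred.

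**5. Demonstration bags.** Each woman sees one of each, so chance is 50% and kappa = 2p − 1, where p is the proportion correct. Arm sizes do not enter.

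**6. Precision in the dummy arm.** Exact (Clopper–Pearson) 95% intervals with 10 users: 2/10 gives 3% to 56%, 5/10 gives 19% to 81%, 10/10 gives 69% to 100%.

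**The case against.** The best reply is that the plan already pairs the percentage with a statistic that corrects for chance. If every woman says 'active', the 80% comes with a kappa of 0. That stands. A reader might infer that the planned figures cannot reveal detection at all; the documents do not support this, because expected kappa is zero without detection and becomes positive when dummy users say 'dummy' more often than active users do.

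A reader might also infer that the objective would be declared failed under perfect blinding, or passed when every dummy was recognised. Neither follows. No blinding threshold is set, and 10.3 calls the study exploratory. The risk is misreading, not a wrong formal decision.

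Third, half of the blinding assessment, the demonstration-bag task, is balanced and sound. That stands too, although it tests side-by-side inspection and not belief after two weeks of use.

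Fourth, rows C and D are equal only on the difference scale; their phi coefficients are 200/√(40·10·45·5) = 0.67 and 200/√(40·10·20·30) = 0.41. Fair: it is no fault for kappa to separate them. Rows E and F do not depend on that choice of scale in the same way, since there kappa fails to separate very different outcomes.

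Finally, kappa is only an example, the guess-by-arm table must exist in order to compute it, and a SAP (not seen) may print that table. This lowers the severity. But the pooled proportion is a firm commitment in the protocol, and the same section specifies by-arm summaries for other endpoints and not for this one.

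**Conclusion.** The point holds for the own-assignment guess only. The pooled percent correct is not interpretable as blinding success: with no detection it lies anywhere between 20% and 80%. Kappa is valid as a check against zero, but under 10:40 its size depends on guessing habit and arm sizes, and it does not identify the unmasked arm.

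The conclusion rests on the planned arm sizes and a two-way answer. The values of q and the outcomes in the table are illustrations, since the protocol gives no guessing rates. It does not extend to the demonstration-bag task, and it does not show that the blinding objective as a whole would be misjudged. This is a cheap improvement to the reporting of a primary objective, not a must-fix.

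**What to change.** In the blinding paragraph of 10.5.2, make the main own-assignment summary the proportion guessing 'active' among dummy users and, separately, among active users, with the difference between them and an exact or score 95% confidence interval, stating that zero corresponds to no detection. Bang's blinding index for each arm may be added. The pooled percent correct and kappa can stay as secondary summaries, and the demonstration-bag analysis needs no change.

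The cost is a few lines of text: no new data, no design change and no extra participants. The downside is that the limited information on about 10 dummy users becomes plain to see; 5/10 would carry an interval of 19% to 81%. The text should say so.
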